Aim 1A: To assess the feasibility of recruiting at least 60 and up to 70 women with early-stage breast cancer who are completing primary treatment in the breast oncology clinic to the study. We will randomize 30-35 women into the intervention group who will view the CCC website and 30-35 women into the control group, who will view an online care plan document. **H1a:** It will be feasible to deploy CCC in an academic breast clinic, as measured by the successful recruitment of at least 60 and up to 70 women (80%) into the study.

Aim 1B: We will assess the acceptability of the CCC website among the 30-35 women randomized to the CCC intervention group. **H1b:** CCC will demonstrate high usability among those who interact with it, as measured by patient-reported ratings of website usability (ease of use, time to completion, amount of information), usefulness, and whether they would recommend it to others.

Aim 2: To explore whether CCC influences patient and provider communication about team-based survivorship care, patient-reported knowledge about team-based survivorship care and follow-up visit scheduling with primary care. **H2a:** Patients who view CCC will report greater knowledge about and better communication with their providers about team-based survivorship care when compared to the control group. **H2b:** A greater proportion of patients who viewed CCC will report scheduling a follow-up visit with their PCP within 3 months compared to those who viewed the control website.

Aim 3: To conduct debriefing interviews with a sample of patients and their providers about their experiences with *ConnectedCancerCare*. We will debrief oncologists, PCPs and patients (in the intervention arm) about the usefulness of the tool and how to best implement it into practice. The results will then be used to further tailor and revise the tool and develop future evaluation plans, as well as guide post-evaluation implementation and ultimate incorporation into the electronic medical record.

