
- 1) **Inform:** This section provides the patient with key facts about survivorship guidelines and what to expect from team-based care.

- 2) **Clarify:** This section provides tailored content to clarify appropriate provider roles in delivering team-based care based on their collected preferences. The preferences outlined in the questionnaire section are used to tailor the content on this page.
- 3) **Communicate:** This section promotes communication with the oncologist and PCP about this topic and includes tips and suggestions on how to communicate with their physicians and get the most out of their clinic visits.
- 4) **To do list for follow-up care and reminders:** This sections outlines for patients what services they will need during survivorship, based on clinical guidelines. Customized alerts will be sent to participants to remind them to schedule their follow-up visits with their PCP, according to the guideline-recommended schedule and to complete their follow-up survey. A total of three reminders for each event have been built into the website program, and subjects are given the choice of how they want to receive reminders (i.e. text or email). Currently, the ConnectedCancerCare website is not linked to MiChart; however, that is a desired feature for future development.

Screen shots of the website content and information on how to access the website directly are included in Appendices 5.

4.4.1. Baseline Questionnaire: After completing the online consent, patients will begin the online questionnaire which collects information that is used to tailor the content of the website. The survey is included in the Appendix. Measures used to tailor the website content include the following:

- a. Knowledge of guidelines for breast cancer follow-up screening and preventive care
- b. Current PCP (yes/no)
- c. Preferences for providers in team-based (PCP or oncologist)
- d. Satisfaction with care coordination at the time of transition
- e. Communication with providers about continuing care
- f. Worry about recurrence

We will also ask patients to provide the contact information for their medical oncologist and primary care physician as part of the baseline questionnaire, which will be used to fax a provider summary to both physicians' offices. The research coordinator will then verify this contact information using MiChart and the internet (for address verification) as needed.

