4.4.2. Provider Summary: The results of the baseline questionnaire will populate a short patient summary and highlight any critical misconceptions, or expectations the patient has about her care and who will be managing it, any gaps in knowledge she has about follow-up care, and a short checklist for her to use to guide her continuing care. Providers of patients randomized to the CCC intervention website will receive a summary based upon patients' answers to the baseline questionnaire for the six areas outlined in the Provider Summary. They include: 1) patient diagnosis and treatment; 2) knowledge of follow-up care; 3) preferences for follow-up care from PCP vs. Oncologist; 4) hormone therapy requirement; 5) personal health concerns; and 6) level of recurrence worry. Providers of patients in the control group will not receive a summary report for these patients.

Figure 5. Provider Summary for Follow-Up Care	
Patient Information Provided	
Diagnosis and Treatment Summary	
Knowledge about Follow-Up Care	
	
 • Questions about diagnosis • Follow-Up services needed
Preferences for Oncologist vs. PCP	
Hormone Therapy (Yes/No)	
	
 • Adherence • Side effects
Personal Concerns	
	
 • Top 3 concerns
Recurrence Worry	

4.4.3. Follow-up Questionnaire: At three months, patients in both groups (intervention and control) will be emailed and prompted to complete a brief, online survey by logging back into the CCC website. The survey includes multiple measures of acceptability and usability in the intervention group only (primary outcomes) as they relate to viewing the tool (described in detail in section 5 below). Also, we will explore the influence of the intervention on secondary patient-reported outcomes including whether they scheduled a visit with their PCP and their knowledge about continuing (survivorship) care, as outlined in section 5 below.

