4.4.4. Patient Contacts: If a patient decides to participate, they will log into the CCC website using the unique assigned ID access code provided with the recruitment letter. Upon initial login, they will consent online, create their account (by inputting their email and phone number) and begin the baseline survey. They will receive one automated email reminder 2 days later if the baseline questionnaire is not completed, and up to 2 personalized phone contacts from the study coordinator within 14 days if the baseline questionnaire remains uncompleted. Upon completion of the baseline questionnaire, participants randomized to the intervention arm will receive weekly reminders via email, and possibly text messages if they opted into texting at account creation to make an appointment with their PCP. Three months from baseline completion, participants will receive a 1-week advance alert email (and a text if they opted in) for the follow-up questionnaire, followed by a second email alert in the next week, indicating the survey's availability on the CCC website. Participants will receive one automated email reminder 5 days later if the follow-up questionnaire is not completed. We will employ a modified version of the Dillman method, which includes up to 3 contacts for follow-up to maximize response rates and to identify non-respondents, that has proven to be successful in our previous work.

4.4.5. Debriefing Interviews: A sample of 8-10 patients who participated in the pilot testing and 4-6 of their physicians (2-3 medical oncologists and 2-3 primary care physicians) will be contacted via phone and invited to participate in debriefing interviews about the usefulness of the tool and future implementation strategies. A question will be included at the end of the follow-up survey which solicits their interest in being contacted after the study ends to discuss their experience with *ConnectedCancerCare* in more detail. For those who respond yes, we will select the first 8-10 people and contact them via phone to conduct a brief 20-minute audiotaped, interview (questions are in the Appendix), to gather their feedback about their experience with the tool.

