We will collect patient-reported outcomes in both the intervention and control groups. We will then explore whether the intervention (compared to control) is correlated with the following measures: Knowledge about continuing care guidelines measured by items used in our previous studies adapted to continuing care (categorical);²⁷ Preferences for team-based care (PCP or oncologist); Satisfaction with care measured by a care coordination question used in previous CanSORT studies tailored to the timing of transition (categorical);⁴⁰ Communication with providers about continuing care measured by an item from the SPARCCS adapted to the patient perspective (categorical).^{18,25} We will explore follow-up visit scheduling (yes/no) using patient-reported measure of whether or not they have scheduled a visit with their PCP since viewing the tool (or control). We will also ask patients whether they have seen their oncologist (yes/no) since viewing the tool and verify their responses using MiChart data.

Aim 3: Debriefing interviews

Guiding questions with prompts will be used to obtain patient and provider feedback (See Appendix for draft interview guide). Patients will be asked about the content of the tool, how they used the tool (or not), and whether it improved their care transition experience. In addition to these questions, providers will also be asked about their experience with the tool summary, how well it fit into their clinical practice, with the goal of understanding how to best imbed the tool into current clinical work-flow.

6. Procedures

6.1. Data Management: We use established human subjects' protection protocols that address the limited use of personal health information, transfer of de-identified datasets within our

institution, storage of information from various data sources and surveillance and response to adverse events. The primary risks of the study are related to breaches in confidentiality and patient concerns about the use of their medical information. We have a long track record of employing the highest standards of patient confidentiality. However, we will respond promptly to any patients or providers who contact the staff or investigators about any concerns related to the study.

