Patient Recruitment for Pilot Testing Patients will be recruited through the Breast Cancer Clinic at the University of Michigan Rogel Cancer Center. Patients eligible for the pilot testing will be those who have recently finished their primary treatment for newly-diagnosed stage I-II female breast cancer and have scheduled their transition visit with the medical oncologist. For the pilot, we will recruit English speaking women with internet access.

Patient and Physician Recruitment for Debriefing Interviews: As stated in section 4.4, a convenience sample of 8-10 patients who participated in the intervention arm and answered that they were willing to be contacted for additional information regarding their experience with using the website on the follow-up survey will be invited to participate in debriefing interviews. We will contact these participants via email and invite them to participate in the debriefing interviews about the usefulness of the tool and future implementation strategies. Debriefing interviews will also be held with 4-6 of their physicians (2-3 medical oncologists and 2-3 primary care physicians) to obtain their views on the usefulness and usage of the tool by their patients and future enhancements.

Sources of Materials: All data to be used in this project will come from: 1) electronic patient surveys (pilot testing), 2) MiChart patient records (participant eligibility), and 3) patient and provider interviews. Survey data will include baseline data collected through the navigation tool, and then follow-up survey data for participants in the intervention three months later. Digital audio recordings will be taken during each physician and patient debriefing interview to be transcribed and analyzed.

8.1. Adequacy of Protection Against Risks: We use established human subjects' protection protocols that address the limited use of personal health information, transfer of de-identified datasets within our institution, storage of information from various data sources and surveillance and response to adverse events. The primary risks of the study are related to breaches in confidentiality and patient concerns about the use of their medical information. We have a long track record of employing the highest standards of patient confidentiality. However, we will respond promptly to any patients or providers who contact the staff or investigators about any concerns related to the study.

9. Data Safety and Monitoring

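### H2b (booking a PCP visit) rests on unverified self-report while only the intervention arm is reminded to book; the MiChart check already planned could cheaply be extended to PCP appointments

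*Combined protocol and SAP*

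**What the plan says.** H2b, in Section 1 under Aim 2, predicts: "A greater proportion of patients who viewed CCC will report scheduling a follow-up visit with their PCP within 3 months". Section 5 (Measures, Aim 2) defines the outcome as "follow-up visit scheduling (yes/no) using patient-reported measure of whether or not they have scheduled a visit with their PCP", asked from the time of viewing the tool or the control page. No check of that answer is described.

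The following sentence in Section 5 adds a second item, on "whether they have seen their oncologist (yes/no) since viewing the tool and verify their responses using MiChart data". MiChart is also one of the sources used to confirm the PCP contact details that women give at baseline (Section 4.4.1). Section 8 (Sources of Materials), however, lists "MiChart patient records (participant eligibility" as the only use of those records.

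The arms differ in what they are prompted to do. Under Section 4.4.4, "participants randomized to the intervention arm will receive weekly reminders via email", and by text for those who opted in, to make a PCP appointment. Section 4.4, in the item on the to-do list, says instead: "A total of three reminders for each event have been built into the website program". Section 4.4.2 adds: "Providers of patients in the control group will not receive a summary report for these patients". Blinding of participants, providers or staff is not mentioned.

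The Study Summary calls the between-arm comparisons exploratory and says they will guide the tool and the planned multi-site trial.

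**The concern.** One arm is told repeatedly to book a visit and is then asked whether it did so; the other arm is not. Women who were reminded and did not book may be more inclined to answer yes than women who were never reminded. That error would differ by arm and favour the intervention, and the data as planned could not reveal it.

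The reminders are part of the intervention, so prompting is not a flaw in itself and a real rise in booking is the intended effect. The difficulty is that self-report alone gives the same signal whether women booked more often or only said so more often. Scheduling a PCP visit is the behaviour the tool is built to change, and the team intends to carry the exploratory results into the design of a larger trial.

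**Working it through.** **The plan's own figure.** The plan gives no rate, effect size or precision for H2b. Its only precision figure, in Section 7.1, is a 95% interval width of 0.374 for acceptability with 30 women and 50% acceptable. The exact (Clopper-Pearson) interval for 15/30 is 0.3130 to 0.6870, width 0.3741, so that figure reproduces. It does not bear on H2b, and everything below is illustration on assumed inputs.

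**Inputs.** From the documents: 30-35 women per arm (Section 4.3) and a chi-square test for categorical outcomes (Section 7, Aim 2). Assumed: two-sided alpha of 0.05 (none is stated); the same true booking rate p in both arms, 30-50%; and a share f of non-bookers who wrongly answer yes, 10-30% in intervention and 0-10% in control. These choices never let control over-report more than intervention, so the direction is assumed too.

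**Spurious difference.** The reported rate in an arm is p + (1 - p) x f. With p equal in both arms, the apparent effect is (1 - p) x (f intervention - f control).

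| True rate p | f intervention | f control | Spurious difference |
|---|---|---|---|
| 0.30 | 0.10 | 0.10 | 0.70 x 0 = 0 |
| 0.30 | 0.10 | 0 | 0.70 x 0.10 = 0.07 |
| 0.30 | 0.30 | 0 | 0.70 x 0.30 = 0.21 |
| 0.50 | 0.20 | 0.05 | 0.50 x 0.15 = 0.075 |
| 0.50 | 0.30 | 0 | 0.50 x 0.30 = 0.15 |

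Over the whole grid the range is 0 to 21 percentage points.

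**Effect on the test.** Exact enumeration of the uncorrected chi-square test, with no over-reporting in control and p from 0.30 to 0.50, gives these chances of a significant result when true booking is equal (about 4-5% without over-reporting):

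| f intervention | 30 per arm | 35 per arm |
|---|---|---|
| 0.10 | 6.9-8.5% | 6.2-9.8% |
| 0.20 | 12.3-19.7% | 12.2-23.0% |
| 0.30 | 21.7-38.1% | 23.4-42.7% |

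**Set against sampling error.** With 30 per arm and both rates at 50%, the 95% half-width for a difference is 1.96 x sqrt(2 x 0.25/30) = 0.253, about 25 points. For 80% power over control rates of 30-60%, the true difference must be about 31-36 points with 30 per arm, or 29-33 points with 35.

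**Whether a verified subset is sound.** PCP details are collected in the baseline questionnaire (Section 4.4.1), and randomisation follows its completion (Section 4.3). A subset defined by the PCP named at baseline is therefore fixed by pre-randomisation information and keeps the randomised comparison. Its size is unknown. If half the women qualified (assumption, 15 per arm), the half-width would be 1.96 x sqrt(2 x 0.25/15) = 0.358, about 36 points.

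**The case against.** The strongest reply is that the outcome is openly declared as self-report and exploratory. No progression rule or sample size depends on it, and the illustrative bias is mostly small beside the sampling error. All of that stands. It limits the weight of the point but does not answer it, because the Study Summary gives these comparisons a use in planning the next trial.

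The remedy also has limits. The in-system share is not stated, women without a PCP fall outside the subset, and agreement by arm will be imprecise. The survey wording is in an appendix that is not shown, so it cannot be seen whether the item asks for an appointment date or other corroboration. These are reasons to keep the verified result descriptive.

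A reader might infer four stronger things that the documents do not support:

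- **That record verification is misdirected to oncologist visits.** Neither H2a nor H2b names oncologist visits. But every participant must be under a breast oncologist at the centre (Section 4.2), so MiChart should hold those visits for all women, and the undefined utilization comparison in Section 7 could include them. Nothing shows that this check displaces a PCP check.
- **That the trial is known to be unblinded.** The documents are silent. Both arms log in to a website and answer the follow-up survey there. Arm-specific reminders and provider summaries make effective masking implausible, but that is an inference.
- **That PCP verification was considered and rejected.** No section discusses it.
- **That an H2b difference would be spurious.** No over-reporting rate is given, and the illustrative range starts at zero.

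**Conclusion.** The point holds as a cheap improvement to an exploratory outcome. H2b is measured by patient report alone, only one arm is reminded to do what is being reported, and the plan has no means of telling a real rise in booking from over-reporting. Under the assumed rates the distortion is 0 to 21 percentage points. That shows what is possible; it is not a prediction. The reminders are a legitimate part of the intervention, and the primary feasibility and acceptability outcomes are untouched. What would be gained is a more trustworthy signal for the planned multi-site trial, and some evidence on whether self-reported scheduling is usable there.

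**What to change.** In Section 5, Aim 2:

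- Extend the MiChart check to PCP appointments booked or attended between baseline and the 3-month survey, for women whose PCP named at baseline is in the health system.
- State that the check covers both arms; the oncologist item as worded mentions only the tool.
- Have existing study staff classify PCPs and abstract appointments, without reference to arm where practical.
- Keep self-report in all women as the H2b measure. Add a descriptive report, by arm in the in-system subset, of MiChart-verified booking and of agreement between self-report and MiChart.

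Amend Section 8 (Sources of Materials), which gives MiChart for eligibility only, so that it agrees with Section 5, and confirm that consent covers the check. Reconcile the reminder descriptions in Sections 4.4 and 4.4.4 (three per event; weekly), since the text does not say how they fit together.

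The cost is modest: extra abstraction in a chart check already planned, an in-system flag for each PCP, and possibly a consent or review-board change. Women with no PCP or an out-of-system PCP remain self-report only, and the verified comparison will be imprecise.

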we will follow the approach used previously by [name] in her iCanDecide recruitment (HUM 62261). The iCanDecide Study was a two-armed randomized controlled trial of an interactive and tailored website with the goal of helping newly diagnosed and early stage breast cancer patients make informed treatment decisions. Employing the same recruitment strategy as used in the pilot study for iCanDecide, a trained clinical research associate will recruit a sample of at least 60 and up to 70 women from the University of Michigan Breast Cancer Clinic who are completing primary treatment for early-stage breast cancer, ages 21-84, and finishing their active treatment visits with their medical oncologist. A study coordinator will identify eligible patients for the pilot testing by reviewing MiChart scheduled oncology visits for patients nearing the end of their treatment and reports from the breast oncology meetings. Patients' eligibility for participation in the study will be verified with the UM breast oncology care team and the PI. Once an eligible patient is identified as being at the end of their primary treatment, the study coordinator will identify their next scheduled visit with medical oncology and plan to be there in person to initiate recruitment. At that visit, the study will be introduced to the patient by the attending oncologist, and those who are interested in participating will then meet with the study coordinator to discuss the following packet of materials: (1) a cover letter written at a 6th grade reading level containing instructions, information about the study including the risks and benefits, their rights as participants and that participation is voluntary; (2) log-in information to access the website which contains the informed consent for them to complete; (3) a copy of the informed consent which they will complete online; (4) information about how to receive a \$20.00 electronic Amazon gift card once subjects have completed the online baseline questionnaire, (5) a local telephone number to call with questions or concerns, and (6) an additional \$20 Amazon gift card included in the study packet to encourage enrollment of participants. For patients' convenience, the study coordinator will provide patients' with the option to view the CCC website or access it via a laptop computer or ipad. When a patient logs into the website, she will be asked to verify personal information and complete the informed consent. The PI and study coordinator(s) will verify subjects' enrollment into the study via their online completion of the consent form and baseline questionnaire, as indicated on the CCC Administrative Dashboard.

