4.5. Time and Events Table

Study Events	Pre-study (after completing primary treatment)	Time 1 (When viewing the website initially)	Time 2 3 months post-baseline questionnaire completion)	Time 3 1-3 months post-follow-up questionnaire completion)
Informed Consent	X			
Baseline Questionnaire	X			
Randomization		X		
View intervention or control website		X		
Follow-up questionnaire			X	
Debriefing Interviews				X

5. Measures

The measures described in detail below were selected after literature review, and were directly informed by our conceptual model and the results of our prior work and pilot data. The measures are described by specific aim below:

Aim 1A: Feasibility

Feasibility will be defined by the successful recruitment of at least 60 women with half randomized to the intervention website and half to the control website over a 9-month time period. Based upon positive response rates of patients in previous studies of survivorship interventions and the iCanDecide pilot trial, we anticipate approaching approximately 87 women in order to achieve a similar response rate of 80% enrollment (n=70). We will also assess the proportion of those successfully recruited who complete the baseline survey and the follow-up survey. In addition, we will capture paradata including participants' average number of page views, and average time on website.

Aim 1B: Acceptability

Acceptability and usability will be defined by asking participants in the intervention arm to rate their experiences with the tool on 5 point Likert-type scales, as follows: (1) CCC was easy to use, (2) CCC was helpful during my transition to survivorship, (3) CCC helped me think about when to see my PCP and when to see my oncologist, (4) I would recommend CCC to other patients, (5) The time it took to go through the website (6) The amount of info.

Based on our prior work, we will use a cut off of 50% of more reporting a score above 3 as acceptable within that domain. We will also examine the distributions within each domain and determine how we can make the next versions of the tool more acceptable to patients as needed. We will then create a summary score of acceptability by averaging the responses to the 6 items, with a score of 3 or more indicating the tool was acceptable to the majority of patients.

Aim 2: Exploratory patient-reported outcomes

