For pilot testing, the study coordinator will assign a unique study ID to each potential participant. A secure, unique ID access code generated by the website will be used by the participants when they log into the website. Access to the password protected, encrypted, study database will be restricted to the principal investigator and selected members of the study staff. For the physician interviews, the digital recordings and transcripts will also be de-identified and stored in password-protected files, which will only be accessible to the principal investigator and study staff. Patient and provider contact information will be kept in encrypted and password-protected files and used until the study and reporting is completed. The research data, which includes health-related data about the participants collected through the CCC intervention, will be stored for the required 7 years in a secured online server after which time the online data files will be electronically and securely deleted from the server, destroying all data.

Weekly meetings with [name] and the study staff will address any adverse events that could result from pilot study participation (e.g. increased anxiety) and patient and physician interview participation. These are anticipated to be rare and will be handled on an individual basis. Any adverse events will be reported to the IRBMED of the University of Michigan according to current IRBMED reporting guidelines.

7. Data Analysis Plan

Aim 1a: Feasibility

To determine feasibility, we will first assess whether we were successfully able to recruit 80% of our target population (N=87) into the study to achieve a maximum sample size of N=70. We will then generate descriptive statistics of the feasibility measures described above, including % of patients who complete each questionnaire, and average number of page views and time on website.

Aim 1b: Acceptability

The distribution within each of the 5 measures of acceptability will be determined and mean scores >3 within each domain will be examined. For any domain that has a mean score below 3, we will then use that information to inform future adaptations of the tool to increase the acceptability. The distribution of the acceptability summary score of will then be assessed and the proportion of patients with a score of 3 or more will be calculated.

Aim 2: Exploratory Patient-Reported Outcomes

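### Section 7 measures the 80% recruitment target against a planning figure of 87, so it tests whether the cap of 70 was reached, not what share of women offered the study joined

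*Combined protocol and SAP*

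**What the plan says.** The plan states recruitment feasibility in three ways.

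- Section 1, hypothesis H1a: feasibility "as measured by the successful recruitment of at least 60 and up to 70 women (80%) into the study".
- Section 5, Aim 1A: "Feasibility will be defined by the successful recruitment of at least 60 women", over 9 months. This is a count with no denominator. The same paragraph explains the 87: "we anticipate approaching approximately 87 women in order to achieve a similar response rate of 80% enrollment (n=70".
- Section 7, Aim 1a: the first analysis is "whether we were successfully able to recruit 80% of our target population (N=87) into the study to achieve a maximum sample size of N=70".

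The other Section 7 feasibility measures are questionnaire completion, page views and time on the website. None of them supplies a denominator for uptake.

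Section 4.2 gives the recruitment flow. It begins "A study coordinator will identify eligible patients for the pilot testing by reviewing MiChart scheduled oncology visits"; reports from the breast oncology meetings are a second source. At the clinic visit the study is "introduced to the patient by the attending oncologist, and those who are interested in participating will then meet with the study coordinator". A woman counts as enrolled once she has completed the online consent and the baseline questionnaire.

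**The concern.** Between Section 5 and Section 7 a forecast becomes a denominator. In Section 5, 87 is roughly how many women the team expects to approach. In Section 7 it is the population of which 80% must be recruited. No section says that exactly 87 women will be approached, or that the observed number approached will replace 87 in the calculation.

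Recruitment feasibility is one of the pilot's primary questions, and Aim 1 looks ahead to a large multi-site trial. Planning sites and accrual time for that trial needs the proportion of eligible women who join when offered the study. As written, the Section 7 percentage gives that proportion only if the forecast happens to be exact. Refusals that are not recorded as they occur may be hard to recover later.

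**Working it through.** **Inputs.** Cap of 70, assumed response of 80% and forecast of 87 (Section 5); the 80% criterion with N=87 (Section 7); minimum of 60 women (Section 5). The documents give no observed number approached, so every such number below other than 87 is an assumption.

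**1. Reproduce the 87.** 70 / 0.80 = 87.5, which agrees with the stated figure apart from rounding. In reverse, 0.80 × 87 = 69.6.

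**2. What the criterion tests.** With the denominator held at 87:
- 69/87 = 79.3% (not met)
- 70/87 = 80.5% (met)

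Enrolment stops at 70, so the criterion is met at exactly one value, the cap.

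**3. Compare the score with uptake.** Uptake = enrolled / approached, with exact (Clopper-Pearson) 95% limits. Score = enrolled / 87. The count column assumes enrolment within 9 months.

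| Approached | Enrolled | Uptake (95% CI) | Score | 80% mark | At least 60 |
|---|---|---|---|---|---|
| 75 | 60 | 80.0% (69.2–88.4) | 69.0% | not met | met |
| 75 | 64 | 85.3% (75.3–92.4) | 73.6% | not met | met |
| 75 | 70 | 93.3% (85.1–97.8) | 80.5% | met | met |
| 87 (plan) | 70 | 80.5% (70.6–88.2) | 80.5% | met | met |
| 100 | 70 | 70.0% (60.0–78.8) | 80.5% | met | met |
| 120 | 70 | 58.3% (49.0–67.3) | 80.5% | met | met |
| 140 | 70 | 50.0% (41.4–58.6) | 80.5% | met | met |

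The score is too high when more than 87 women are approached and too low when fewer are. It is right only at 87.

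**4. How easily the criterion misleads.** These are exact binomial chances of reaching 70, treating women's decisions as independent with a common probability:
- 120 approached at 60% uptake: 0.68
- 140 approached at 50% uptake: 0.53
- 80 approached at 85% uptake: 0.33
- 75 approached at 85% uptake: 0.02

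The number approached drives the result at least as much as women's willingness to join.

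**5. The two pass marks.** 60/87 = 69.0%, so the Section 5 minimum fails the Section 7 mark. Sixty is 80% of 75 (60/0.80 = 75), not of 87. The single 80% that H1a attaches to the whole range of 60 to 70 cannot hold on one denominator.

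**6. Where an observed count should start.** The plan does not say whether approaching a woman means the oncologist's introduction or the meeting with the coordinator. Suppose 87 women met the coordinator and 70 enrolled. If a share f of those introduced had expressed interest, uptake among those introduced is (70/87) × f. For f = 90%, 80% and 70% (assumed) this is 72.4%, 64.4% and 56.3%, against 80.5% when counted from the coordinator meeting. Starting the count at the coordinator can only overstate uptake.

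**The case against.** The strongest reply is that Section 7 loosely repeats the Section 5 forecast. The same three figures (87, 80%, 70) appear in both places. Section 5 calls the 80% a response rate, which ordinarily means enrolled over approached. No sentence says the divisor stays at 87 if 120 women are approached, and if about 87 are approached, as planned, the score is the true rate. That may well be the intent. It does not settle the matter, because the only denominator the analysis plan names is 87.

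Four further objections stand and limit the point.

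- A reader might infer that the oncologist's introduction distorts the Section 7 score, perhaps in both directions. It cannot: a rate divided by a fixed 87 does not depend on who was filtered out earlier. The filter matters only once an observed denominator is used, and then only upward.
- A reader might infer that the plan would declare 60 of 75 a recruitment failure. That follows only from the Section 7 mark, since 60 women meet the Section 5 definition.
- A reader might infer that women who decline to the oncologist are lost to any count. The documents do not support this. The coordinator identifies eligible women before the visit, study IDs are assigned to potential participants (Sections 6.1 and 9.1), and recruitment is reviewed weekly against expectation (Section 9.2). The counts look obtainable, but the analysis plan does not use them.
- Dividing by every eligible woman seen in the full 9 months would also mislead. If the cap were reached early, women who could no longer join would count against uptake.

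The appendices were not available, so a screening log there cannot be excluded. It would not change the N=87 in Section 7.

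**Conclusion.** The point holds for the 80% rate in Section 7 and should be fixed. As written, the rule tests whether the cap of 70 was reached, and it misstates uptake whenever the number approached is not 87. With 70 enrolled, the score is 80.5% whether uptake was 93.3% (75 approached) or 50.0% (140 approached). The direction and size of any actual error depend on a number the documents do not give, so these are illustrations and not predictions.

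A reader might go further and conclude that the feasibility assessment as a whole fails. The documents do not support that. The Section 5 count of at least 60 women in 9 months needs no denominator and remains interpretable, and nothing makes the 80% result a formal gate for the larger trial.

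**What to change.** In Section 7, Aim 1a, replace N=87 with an observed denominator:

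- **Main rate:** enrolled divided by eligible women to whom the study was introduced, by the oncologist or the coordinator, up to the date enrolment closes, with an exact 95% CI. Count from the oncologist's introduction.
- **Supporting rate:** enrolled divided by all eligible women identified, from MiChart and the breast oncology meeting reports, up to the same date. Give the numbers not approached, declined to the oncologist, declined to the coordinator, and with baseline not completed.
- **Planning figure:** keep 87 in Section 5 as the expected number to approach, and label it so.
- **Pass mark:** state how the 80% criterion relates to the Section 5 definition of at least 60 women in 9 months, and align H1a with it.

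The cost is a few lines of text and a small running tally, most of which can come from the list the coordinator already compiles. Oncologists would need to report introductions that ended in refusal. The reported rate may be lower than under the present rule. Design, sample size and what participants do are unchanged.
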